8.3 Hospitalization/Surgery/Discharge

Subjects will be admitted to the hospital according to the Investigator's standard for non-cervical spine surgery. Prophylactic antibiotics may be administered prior to surgery in accordance with the surgeon's standard of care and anesthesia will be administered per standard operating procedures. The system will be implanted in accordance with methods detailed in the instructions for use for the MESA Rail Deformity System.

Data points required on the Operative case report form must be documented at the time of surgery. Intra-operative adverse events must be recorded and documented on an Adverse Event case report form.

A Subject may be excluded from the study intra-operatively at the discretion of the Investigator if unexpected findings/occurrences dictate deviation from the intended study procedure. Justification for an intra-operative exclusion and alternative surgical procedure must be fully documented in the subject's medical record and on the Study Exit case report form. A subject who is excluded intra-operatively will be considered an overall treatment failure.

If the patient experienced an adverse event(s) during the hospitalization it should be documented and recorded on an Adverse Event case report form. The subject may be instructed to return to normal activity at the discretion of the Investigator.

Additional post-operative restrictions may be imposed according to the standard of care normally utilized by the Investigator. In addition, subjects should be instructed to notify the Investigator if experiencing untoward events including but not limited to noticeable pain, numbness, tingling, or weakness that does not decrease with rest, swelling of the lower extremities that does not decrease, or increased pain, erythema, edema or drainage from the surgical incision. The Investigator should then determine if an evaluation is warranted.

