9.1.3 Subsequent Surgical Interventions

The cause for subsequent surgical interventions should be listed as a serious adverse event.

Subsequent surgical interventions are classified as follows:

Revision: a procedure that adjusts or in any way modifies the original implant configuration. A revision may also include adjusting the position of the original configuration.

Removal: a procedure where all of the original system configuration are removed with or without replacement.

Supplemental Fixation: a procedure in which additional instrumentation not under study in the protocol is implanted.

Re-Operation: any surgical procedure at the involved level that does not require removal, modification, or addition of any components to the system.

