12.2 Study Hypothesis

The primary objective of this study is to evaluate the effectiveness of the MESA Rail Deformity System in terms of restoring and maintaining thoracic kyphosis in the treatment of patients with symptomatic AIS. The primary effectiveness endpoint is the rate of overall subject success (minimal loss of thoracic kyphosis) at 24 months. The primary hypothesis of this trial is that the clinical performance of the K2M MESA Rail implant is non-inferior to the clinical performance achieved and achieved with fusion utilizing a standard Ø5.5mm or Ø4.5mm CoCr rod.

A PubMed literature review was conducted to assemble relevant publications utilizing results from posterior instrumentation fusion surgeries in patients with AIS. Searches included all peer-reviewed journals published between January 2000 and March 2013. Sample sizes, patient populations, evaluated variables, results, and recorded complications were assessed for each selected article. Only data regarding thoracic kyphosis measurements of single-stage posterior fusion cases were incorporated into the thoracic kyphosis table used for statistical analysis. Articles were entirely excluded from the statistical analysis if results combined data from multi-stage cases or if data were extracted through meta-analysis.

The following table gives the preoperative thoracic kyphosis measurements as well as the thoracic kyphosis measurements collected at the last follow-up period from all relevant posterior fusion surgeries in patients with AIS:

| Thoracic Kyphosis | | | | | | | | | |
|----------------------------------|-----|-------|------|---------|------|------|------|---------------------|-------------|
| paper # | n | Preop | | Last FU | | Diff | | Mean difference x N | Std Dev x N |
| | | Mean | SD | Mean | SD | Mean | SD | | |
| 1 ¹ | 9 | 31.9 | 10.4 | 26.0 | 9.8 | 5.9 | 10.1 | 53.1 | 90.9 |
| 1 | 3 | 31.0 | 9.5 | 29.7 | 5.5 | 1.3 | 7.5 | 3.9 | 22.5 |
| 1 | 34 | 28.2 | 13.0 | 26.5 | 11.0 | 1.7 | 12.0 | 57.8 | 408.0 |
| 1 | 9 | 23.0 | 8.0 | 23.0 | 11.0 | 0.0 | 9.5 | 0.0 | 85.5 |
| 1 | 60 | 26.7 | 13.0 | 25.0 | 9.6 | 1.7 | 11.3 | 102.0 | 678.0 |
| 1 | 31 | 22.8 | 11.0 | 25.7 | 8.8 | -2.9 | 9.9 | -89.9 | 306.9 |
| 2 ² | 83 | 23.0 | 12.0 | 20.2 | 8.4 | 2.8 | 11.4 | 234.9 | 946.2 |
| 3 ³ | 111 | 29.0 | 14.0 | 23.0 | 10.8 | 6.0 | 12.2 | 666.0 | 1354.2 |
| 3 | 299 | 22.0 | 14.1 | 22.0 | 10.3 | 1.0 | 5.0 | 299.0 | 1495.0 |
| Weighted Mean Difference and SD: | | | | | | | | 2.1 | 8.4 |

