The study hypothesis is that the RAIL system is superior to other systems in Thoracic Kyphosis Correction. The hypotheses can be written:

$$\begin{aligned} H_0: \mu_R &< OPC - \delta \\ H_1: \mu_R &\geq OPC - \delta \end{aligned}$$

where μ_R is the mean Thoracic Kyphosis Correction of the RAIL system and OPC is the Objective Performance Criteria of 2.2 and $\delta = 2$ degrees.

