12.5 Analysis of Primary Endpoint

The primary effectiveness endpoint will be evaluated by a two-sided exact test of the MESA Rail implant success rate (mean thoracic correction) against the literature reported mean thoracic correction of 2.2 degrees.

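### The rule that makes an intra-operative exclusion a treatment failure cannot be applied to a primary analysis of mean degrees, and kyphosis values after later surgery on the construct have no rule

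*Combined protocol and SAP*

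**What the plan says.** **The failure rule.** Section 8.3 lets the investigator exclude a subject during surgery ("A Subject may be excluded from the study intra-operatively at the discretion of the Investigator"), has the reason recorded on the Study Exit form, and adds: "A subject who is excluded intra-operatively will be considered an overall treatment failure".

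**The endpoint as a rate.** Section 12.2 says: "The primary effectiveness endpoint is the rate of overall subject success (minimal loss of thoracic kyphosis) at 24 months". It gives no number of degrees for minimal loss and no reference success rate.

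**The endpoint as a mean.** The formal hypotheses in 12.2 concern the mean correction, where "OPC is the Objective Performance Criteria of 2.2" and the margin is 2 degrees. Section 12.3 sizes the study with a one-sample t-test on that mean. Section 12.5 merges the two forms, calling for a "two-sided exact test of the MESA Rail implant success rate (mean thoracic correction) against the literature reported mean thoracic correction of 2.2 degrees".

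**Who is analysed.** Under 12.4 the ITT set is everyone enrolled, and under 8.1 enrolment happens at consent. The per-protocol set removes only eligibility and consent violations.

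**Later surgery.** Section 9.1.3 defines revision, removal (with or without replacement), re-operation and supplemental fixation, the last as: "Supplemental Fixation: a procedure in which additional instrumentation not under study in the protocol is implanted". Sections 12.6 and 12.7.1 tabulate revision and removal rates descriptively. No section says what happens to the primary endpoint after any of these, and none makes them a reason to exit. Section 7.3 expects 24 months of follow-up.

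**The concern.** A subject can be declared a failure only if the endpoint has a failure category or a score for failure. The mean that is tested and powered has neither. If the plan is followed as written, subjects it calls failures have no value to contribute, and the rule in 8.3 has no effect on the primary result.

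Later surgery raises a related problem. A 24-month angle measured after hardware was removed, adjusted or added describes the initial construct plus the later procedure, or no construct at all. With no rule, that angle would enter the mean as a Rail result.

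The advantage the study is built to detect is only 4.0 - 2.2 = 1.8 degrees, so a few subjects handled one way or another could matter. An open choice can also be settled after the data have been seen.

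**Working it through.** **1. What the design was sized on.** Inputs from 12.3: mean 4.0, comparator 2.2, SD 8.4, two-sided alpha 0.05, power 80%, attrition about 15%.
- Normal approximation: n = (8.4 × (1.960 + 0.842) / 1.8)² = 170.9, so 171.
- Noncentral t: n = 173, power 0.8003. This matches the plan.
- Enrolment: 173 / 0.85 = 203.5, so 204. This also matches.

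The sample size is therefore that of a continuous mean. A success-rate version cannot be computed, because neither a threshold nor a reference rate is given.

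**2. What happens to each kind of subject.**
- *Intra-operative exclusion:* in the ITT set (8.1, 12.4), failure by 8.3, out of the study, no 24-month film expected. Section 12 has no imputation or missing-data rule, so a mean would in practice omit the subject.
- *Removal, revision or supplemental fixation:* still in the study, film due at 24 months. No rule excludes or replaces the value, so by default it is averaged. The per-protocol set does not change this.

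**3. The sign.** The literature table in 12.2 takes pre-operative minus last follow-up; its first row is 31.9 - 26.0 = 5.9, so a positive number is kyphosis lost. The hypotheses call the parameter correction, with larger values better. Until one convention is chosen, an unfavourable value is not defined. Steps 4 and 5 assume that larger is better.

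**4. Illustrative shift in the mean.** The documents give neither a frequency of these events nor a score for them. Assume a share f of 2-5% (about 4-10 of 204). Shift = f × (4.0 - score), or f × assumed deficit.

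| Failures scored as | f = 2% | f = 5% | Share of 1.8 |
|---|---|---|---|
| 2.2 (deficit 1.8) | 0.04 | 0.09 | 2-5% |
| 0 (deficit 4.0) | 0.08 | 0.20 | 4-11% |
| deficit 10 (at 2%) to 15 (at 5%) | 0.2 | 0.75 | 11-42% |

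The last row assumes a deficit of 1.2 to 1.8 SDs (10/8.4 to 15/8.4), for which the documents give no source.

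**5. Illustrative power with 173 evaluable.** Let g be the failure fraction and v the score. Mean = (1 - g) × 4.0 + g × v. SD = √[(1 - g) × 8.4² + g(1 - g)(4.0 - v)²]. The test is against 2.2.

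| Failures among 173 | Dropped at random | Scored 2.2 | Scored 0 | Scored -4.4 (4.0 - 8.4) |
|---|---|---|---|---|
| 2 (1%) | 79.6% | 79.6% | 78.3% | 75.5% |
| 5 (3%) | 78.9% | 78.8% | 75.6% | 67.9% |
| 9 (5%) | 77.9% | 77.8% | 71.6% | 56.6% |
| 17 (10%) | 75.8% | 75.7% | 62.6% | 33.2% |

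At about 1% the handling matters little under most scorings. At 5% it moves power from 77.9% to 56.6%.

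**The case against.** Several points on the other side stand.

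- A reader might infer that the endpoint has no failure state at all. Sections 12.2 and 12.5 do name a success rate, and the failure rule in 8.3 fits it. The defect is that this rate is undefined and then merged with a mean.
- Nor do the documents say that excluded subjects drop out, or that re-operated subjects keep their values. Both are the likely default where the plan is silent.
- It is too broad to say that every value after later surgery comes from other hardware. A revision may only adjust the existing construct, supplemental fixation may leave the Rail in place, and removal may be without replacement. Section 8.3.1 already provides for a unilateral Rail with a different rod on the other side.
- A reader might infer that both paths favour the Rail. This is not shown. The sign is unsettled; intra-operative exclusions need not reflect device failure or poor kyphosis; a removal without replacement could worsen the mean; dropping a random subset leaves the expected mean at 4.0; and nothing is said about how the literature series handled re-operations.
- Keeping observed values after re-operation is a recognised treatment-policy approach, not a bias in itself.
- Revision and removal rates are already to be tabulated, and the causes of later surgery are recorded as serious adverse events.

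These points limit what can be said about bias. They do not make the 8.3 rule executable, and they do not supply the missing handling rules. The existing tables also give no combined proportion that includes intra-operative exclusions, and no confidence interval.

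**Conclusion.** The point holds as a contradiction and a gap in the plan. The failure rule in 8.3 has no means of execution in the hypotheses, sample size or test. The ITT members it covers would in practice be absent from the mean, and the handling of values after removal, revision or supplemental fixation is unspecified.

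The documents do not establish an upward bias or a particular size. The shift of 0.04 to 0.75 degrees rests wholly on an assumed 2-5% event share, on the assumed scores, and on larger values being better. The upper end, 42% of the 1.8-degree effect, needs both the highest share and the largest deficit and should not be read as an estimate. The change should be made because the plan's own rule currently has no effect and the choice is open; the primary test and the sample size need not change on this account.

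**What to change.** 1. Reconcile 8.3, 12.2 and 12.5: state the primary endpoint once, as a mean or as a rate with a threshold and reference rate, and fix the sign of correction. Say how the failure rule applies to the endpoint chosen.
2. Beside the primary mean, report the proportion of all attempted Rail implantations that end in intra-operative exclusion, removal, revision or supplemental fixation, with an exact 95% CI.
3. Pre-specify one sensitivity analysis that repeats the comparison with 2.2 degrees after giving all such subjects an unfavourable value, for example the least favourable decile of observed change, defined once the sign is fixed. Keep the observed-value analysis as the treatment-policy result. The decile is one choice among several; it should be settled before the data are seen.

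**Cost:** changed wording, one extra table and one extra run. The Study Exit, Adverse Event and Operative/Discharge forms listed in 8.11.1 already collect the events. The supporting result may be less favourable than the headline mean.

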8.3.1 Surgery/Hospital Discharge Evaluation

Surgery Data

- Date of Hospital Admission
- Date of Surgery
- Date of Hospital Discharge
- Implanting Surgeon
- System Details (screw and rod size, unilateral vs. bilateral use of the MESA Rail, contra-lateral K2M rod system used (if bilateral MESA Rails not used), connector use, etc.)
- Surgery Detail/Concomitant Procedures
- Surgery Time (initial incision to closure)
- Anesthesia Time
- Perioperative Antibiotic Use
- Estimated Blood Loss
- Adverse Event Assessment (surgery through discharge)

8.4 Post-Operative Follow-Up Visits

All subjects will be required to return for follow-up visits at initial post-op, 3 months, 6 months, 12 months, and 24 months post-procedure. (A "wound check only" visit does not require data collection unless there is an adverse event. Then this would be captured as an Unscheduled Visit, and an Adverse Event CRF would be completed.)

Data collected at each follow-up visit must be confirmable by source documents and the appropriate case report forms must be completed. All patient questionnaires should be completed at the visit, preferably prior to the patient interacting with the Investigator or other clinical staff. Requirements at each post-operative follow-up visit are as follows:

8.4.1 Follow-Up Evaluations and Data – Post-Op through 24 Months

- Work/School Status (including release for return to work/school) and current symptoms
- Medication Taken for Spine Problem since Last Contact
- Symptom Directed Neurological Examination
- AP and Lateral X-rays (initial post-op, 6 Months, 12 Months and 24 Months)
- SRS-22r (6 Months, 12 Months and 24 Months)
- Back and Leg VAS
- Patient Satisfaction (12 and 24 Month only)
- Odom's Criteria (24 Month only)
- Adverse Event Assessment
- Study Exit

8.5 Unscheduled Follow-Up Evaluation

Subjects may return to the clinic at a time point that is not a scheduled follow-up visit. If the Investigator determines that the return visit is related to the study device or procedure, the unscheduled visit portion of the Follow-Up case report form should be completed. If a subject requires a device or procedure related re-operation including supplemental fixation, revision and/or device removal as a result of an unscheduled visit, the Sponsor should be notified immediately and an Adverse Event case report form should also be completed. The requirements for an unscheduled visit are as follows:

- Reason for Visit/Current Symptoms/Pertinent History
- Symptom Directed Neurological Examination
- X-rays as needed (if done, a minimum of AP and Lateral)
- Adverse Event Assessment

8.6 Schedule of Evaluations

8.6.1 Schedule of Evaluations

| Interval → Assessment ↓ | Pre-Op | Operative /Discharge | Initial F/U (2-8 wks) | 3 Mo F/U (± 2 wks) | 6 Mo F/U (± 1 mo) | 12 Mo F/U (± 2 mo) | 24 Mo F/U (± 2 mo) | Unscheduled Visit |
|---------------------------------------|--------|----------------------|-----------------------|--------------------|-------------------|--------------------|--------------------|-------------------|
| Informed Consent | X | | | | | | | |
| Inclusion/Exclusion | X | | | | | | | |
| Demographics | X | | | | | | | |
| Pertinent History | X | | | | | | | X |
| Current Symptoms | X | | X | X | X | X | X | X |
| Work/School Status | X | | X | X | X | X | X | |
| Medications for Spine Problems | X | | X | X | X | X | X | X |
| Neurological Examination | X | | As needed | As needed | As needed | As needed | As needed | As needed |
| AP & Lateral X-rays | X | | X | | X | X | X | If needed |
| Right and Left Lateral Bending X-rays | X | | | | | | | |
| Back and Leg VAS | X | | X | X | X | X | X | |
| SRS-22r | X | | | | X | X | X | |
| Hospitalization and Surgery Data | | X | | | | | | |
| Adverse Event Assessment | | X | X | X | X | X | X | X |
| Patient Satisfaction | | | | | | X | X | |
| Odom's Criteria | | | | | | | X | |
| Study Exit | | | | | | | | X |

8.7 Pregnancy during Study Participation (as appropriate)

If a subject becomes pregnant during the study, the sponsor should be notified as soon as possible. The subject will remain in the study, but during the pregnancy the study follow-up visit(s) will be modified to exclude the X-ray imaging requirements. At follow-up visits after the pregnancy, the required X-rays should again be performed. Information related to the pregnancy and outcome should be maintained by the site and documented by the Sponsor in monitoring reports during periodic visits.

8.8 Protocol Deviations

The Protocol must be followed closely, and the Investigators should not deviate from the Protocol unless in the opinion of the Investigator a deviation from the protocol is in the best interest of safety for the subject. A deviation from the Protocol should be reported to the sponsor as soon as possible after the deviation is noted. In addition, during routine monitoring visits the monitor may determine a protocol deviation and initiate the protocol deviation process. All protocol deviations must be documented on a Protocol Deviation case report form. For the scientific integrity of the study, protocol deviations must be kept at a minimum. If a site has an unacceptable number of protocol deviations that cannot be explained due to patient safety, the issue will be discussed with the site and corrective action will be considered.

In the event a patient questionnaire is not completed during a visit, permission may be obtained from the Sponsor to have that questionnaire mailed into the site within a reasonable amount of time.

8.9 Subject Lost to Follow-Up

Every attempt will be made to have all subjects complete the follow-up visit schedule as specified in the protocol. A subject will not be considered lost to follow-up unless efforts to obtain compliance are unsuccessful. If a subject misses a follow-up visit, the site must document attempts to contact the subject by phone twice. If both contact attempts are unsuccessful, a certified letter from the Investigator must be sent to the subject's last known address indicating the subject's commitment to the study and site contact information to arrange a visit. If the subject does not respond, only then will the subject be considered lost to follow-up. If a subject is lost to follow-up, a Study Exit case report form, including a full description of the attempts to locate the subject, must be completed.

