2.7 Mitigation of Risks

Operative and acute periprocedural risks for the patients enrolled in this study are mitigated by restricting the use of the device to skilled neurological and orthopedic spine surgeons trained and experienced in the proper surgical technique to implant the respective devices. Long-term risks such as device disengagement/failure and pseudoarthrosis are mitigated by proper patient selection and implanting the devices in accordance with the Surgical Technique Manual for the MESA Rail Deformity System and use of the surgical instruments provided by K2M and by following accepted standard of care for this AIS population.

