8.11.1 List of Case Report Forms

- Inclusion/Exclusion
- Pre-Operative
- Operative/Discharge
- Follow-Up Visit which includes:
 - Initial Post-Op Follow-Up Visit (between 2-8 weeks post-op)
 - 3 Month Follow-Up Visit \pm 2 Weeks
 - 6 Month Follow-Up Visit \pm 1 Month
 - 12 Month Follow-Up Visit \pm 2 Months
 - 24 Month Follow-Up Visit \pm 2 Months
 - Unscheduled Visit
 - Odom's Criteria (24 Month Visit Only)
- Patient Questionnaires:
 - Back Visual Analog Scale (VAS) and Leg Visual Analog Scale (VAS)
 - SRS-22r
 - Patient Satisfaction
- Adverse Event
- Protocol Deviation
- Study Exit

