12.3 Sample Size

If the mean Thoracic Kyphosis Correction of the RAIL system is 4.0 with a standard deviation of 8.4, then 173 subjects provides 80% power to detect a statistically significant difference between the mean correction and the OPC of 2.2 using a two-sided one-sample t-test at a significance level of 0.05. In order to account for approximately 15% attrition, based on clinical experience, 204 subjects will be enrolled.

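### Section 8.9 exits an unreachable subject after any single missed visit, with no new attempt required at later visits and no route back before the 24-month endpoint

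*Combined protocol and SAP*

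**What the plan says.** All references are to the combined protocol and SAP.

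- **Aim (8.9).** "Every attempt will be made to have all subjects complete the follow-up visit schedule as specified in the protocol".
- **Trigger (8.9).** "If a subject misses a follow-up visit, the site must document attempts to contact the subject by phone twice". The sentence does not distinguish between visits, so any one of them starts the process.
- **Next step (8.9).** "If both contact attempts are unsuccessful, a certified letter from the Investigator must be sent".
- **Declaration (8.9).** "If the subject does not respond, only then will the subject be considered lost to follow-up". No time to wait for a reply is given.
- **Consequence (8.9).** "If a subject is lost to follow-up, a Study Exit case report form, including a full description of the attempts to locate the subject", must then be completed.

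Section 8.9 requires no further attempt when the next scheduled visit falls due and does not provide for a subject who makes contact again. Section 7.3 sets participation at 24 months after surgery. The schedule in 8.6.1 has visits at 2-8 weeks and at 3, 6, 12 and 24 months, the last with a window of 2 months either way. Section 9.2 ties adverse event recording to the subject's participation. Section 12.2 places the primary endpoint at 24 months. On attrition, section 12.3 says: "In order to account for approximately 15% attrition, based on clinical experience, 204 subjects will be enrolled".

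**The concern.** The visit that triggers the exit may matter little in itself, while the data that can be lost with it matter a great deal. The 3-month visit has no X-ray and no SRS-22r (8.4.1, 8.6.1), so missing it costs nothing on the primary endpoint. Missing it and not answering, however, leads to a Study Exit form 21 months before the primary assessment.

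Two things are at stake. The first is the 24-month kyphosis value of subjects who could have been reached at a later visit. Section 12.4 analyses effectiveness on all enrolled subjects, yet section 12 gives no rule for a missing 24-month value. The second is late safety information. Section 2.7 says "Long-term risks such as device disengagement/failure and pseudoarthrosis are mitigated by proper patient selection", so the plan itself treats these as long-term risks, and a subject whose participation has closed may not be asked about them.

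The plan handles another interruption differently. Under 8.7 a subject who becomes pregnant stays in the study, omits the X-rays for that period and resumes them afterwards. Section 8.9 has no such provision for a missed visit.

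**Working it through.** **1. The plan's own figures.** Section 12.3 gives a mean of 4.0, an SD of 8.4, a comparator of 2.2, and a two-sided one-sample t-test at 0.05. The standardised difference is (4.0 - 2.2)/8.4 = 0.214. With the noncentral t distribution, n = 173 gives power 0.800, as stated. Inflating for 15% attrition, 173/0.85 = 203.5, which rounds up to 204, also as stated. The allowance is 204 - 173 = 31 subjects.

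**2. Follow-up lost on exit.** Nominal month 24 minus the time of the missed visit:

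| Missed visit | Calculation | Months lost |
|---|---|---|
| Initial (window closes at 8 weeks, about 1.8 months) | 24 - 1.8 | about 22 |
| 3 months | 24 - 3 | 21 |
| 6 months | 24 - 6 | 18 |
| 12 months | 24 - 12 | 12 |

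For the initial visit, the 22-to-26-month window for the last visit gives a range of 20.2 to 24.2 months.

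**3. How many could be exited before month 24.** The documents give no visit-level rate. Let q be the proportion of subjects still in follow-up who, at each of the four earlier visits, miss the visit and answer neither the calls nor the letter (an assumption). The proportion exited before month 24 is 1 - (1 - q)^4:

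- q = 3%: 1 - 0.97^4 = 11.5%
- q = 4%: 1 - 0.96^4 = 15.1%
- q = 5%: 1 - 0.95^4 = 18.5%

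At q = 4% this equals the allowance (31/204 = 15.2%).

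**4. What part of that is due to the rule.** If r is the share of exited subjects who would have attended at 24 months had contact been tried again, the loss attributable to the rule is r × [1 - (1 - q)^4]. The documents give no r. It lies between 0 and 1, so at q = 5% the attributable loss is anywhere from 0 to 18.5%.

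**5. Effect on power if total attrition exceeded the allowance** (rates above 15% are assumptions):

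| Attrition | Subjects left of 204 | Power |
|---|---|---|
| 15% | 173 | 80.0% |
| 20% | 163 | 77.6% |
| 25% | 153 | 75.0% |

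**The case against.** The strongest reply is that 8.9 sets a minimum before loss may be declared and does not instruct sites to stop. It opens with a commitment to full follow-up, it restricts premature declaration, and a subject who answers either call or the letter is not exited. The last point stands and limits the concern to non-responders. The opening commitment stands as an aim but adds no steps; the only steps listed are two calls, a letter and the form.

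Four stronger readings are tempting, and the documents do not support them.

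- **That exit bars all later data.** No section says so. Section 8.5 allows unscheduled returns and calls for immediate notice to the sponsor of a device- or procedure-related re-operation. Section 5.2 intends to capture all device failures, and 9.2 follows adverse events until resolved or stable. Set against the link in 9.2 between recording and participation, the status of an exited subject is unclear.
- **That exited subjects count as event-free.** Section 12.4 puts safety on all enrolled subjects, but 12.6 tabulates rates at each follow-up interval without defining the denominator. Event-free counting is one possible result.
- **That 11.5% to 18.5% is the harm done by the rule.** That range counts every unreachable subject under an assumed q, including those no further call would have recovered.
- **That the loss is selective.** Subjects may stay away because they are well or are treated elsewhere, but the documents give no evidence either way.

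**Conclusion.** The concern holds as a weakness in retention. Followed as written, 8.9 closes out a non-responding subject after one missed visit and requires no later attempt, although the outcome that matters most is measured at 24 months. For each such subject about 12 to 22 months of follow-up and the primary value can be lost. This rests on reading the Study Exit form, together with 9.2, as the end of routine data collection. That is the natural reading but not an express rule.

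The total effect cannot be sized, because neither the rate of non-response per visit nor the share who would have returned is given. The sample size is not in error: 173 and 204 both reproduce, and a rise in attrition to 20% would cost only 2.4 percentage points of power (80.0% to 77.6%). The case for change rests on avoidable missing 24-month and late safety data, and on the low cost of preventing it.

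**What to change.** Amend section 8.9 as follows:

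- A missed visit with failed contact is recorded as a missed visit, and the subject stays in the study.
- Contact is attempted again at every remaining visit window.
- Lost-to-follow-up status, and the Study Exit form for non-contact, apply only once the 24-month window (24 months plus 2 months) has closed without contact.
- At any later contact the site collects interim adverse events and subsequent surgical interventions, and the subject resumes the schedule.

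Withdrawal of consent stays under 8.10, unchanged. The cost is protocol wording, a few more calls per missing subject and site records kept open longer; no visits are added. The change does not settle how section 12 handles subjects who remain unreachable: the denominator for interval adverse event rates in 12.6 and the treatment of missing 24-month values still need to be stated there.
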